Explorative Objectives	
 1. To determine the effect of study drug on comprehensive geriatric assessment domains. 2. To determine the effect of the study drug on short-term and long-term health-related quality of life (HRQOL) 3. To evaluate if positive status for Stat5 activation in the paraffin-embedded tissue sections of the most recent biopsy specimen has a trend to predict biochemical response to pacritinib treatment
Study Design	Single-arm, open-label study.
Study Agent	Pacritinib 200 mg BID.
Number of Subjects	N= 46. The first cohort of the study will enroll 10 patients. Enrollment to the second cohort(n=36) would be dependent on the response noted in the first cohort and funding.
Estimated Time to Complete Enrollment:	Approximately 12 months for the first 10 patients and 36 months for total study.

Inclusion criteria	
 ▪ Histologically or cytologically confirmed prostate adenocarcinoma. ▪ Prior radical prostatectomy or definitive radiation therapy. ▪ Biochemically recurrent prostate cancer with PSA doubling time \leq 9 months at the time of study entry. ▪ Prior adjuvant or salvage radiation or not a candidate for radiation based upon clinical assessment of disease characteristics and patient comorbidities. ▪ Screening PSA $>$ 0.5 ng/mL. ▪ No definitive evidence of metastases on screening imaging per the judgment of the investigator. Pelvic lymph nodes measuring 1.5 cm or less in short axis diameter are allowed. ▪ Screening serum testosterone $>$ 50 ng/dL. ▪ Eastern Cooperative Oncology Group (ECOG) Performance Status grade 0-1 or Karnofsky Performance Status \geq 70. ▪ Age \geq 18 years. ▪ Absolute neutrophil count \geq 500/ μL, ▪ Agrees to use a condom (even men with vasectomies) and another effective method of birth control if he is having sex with a woman of childbearing potential. ▪ Adequate organ function. ▪ Left ventricular cardiac ejection fraction of \geq 50% by echocardiogram or multigated acquisition scan. ▪ Adequate coagulation defined by prothrombin time/international normalized ratio and partial thromboplastin time \leq 1.5x ULN.

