Pacritinib Dosage Modifications	Pacritinib dosage may be interrupted or modified for pacritinib-related hematologic toxicities, hemorrhage, severe infections, cardiac toxicities (including QTcF interval prolongation and reduction in ejection fraction), diarrhea, and other pacritinib-related nonhematologic toxicities. Pacritinib dosage may also be held for invasive procedures or at the discretion of the investigator. Refer to Section 5.2 for pacritinib dosage management guidelines.
Safety	Safety and tolerability will be assessed primarily by the incidence, severity, and change from baseline in safety parameters, such as treatment-emergent AEs (TEAEs; including SAEs), laboratory values, cardiac assessments, and vital signs.

STUDY SCHEMA

RT-radiation therapy
BID- twice a day
ADT-androgen deprivation therapy
LN-lymph node
DT-doubling time

STUDY CALENDAR

Study Assessments	Screening ¹		Cycle 1 ²		Cycle 2		Cycle 3		Cycle 4		Cycle 5		Cycle 6 and beyond (Treatment till progression)		End of treatment ¹ (EOT) visit ± 7 ⁴	Follow-up (2 years) ³
	Day - 30 to -1	Day - 30	Each Cycle (28 days)												30-day post-last dose Safety Visit (±7 days)	Every 6 months post EOT visit (±21 days)
Informed consent	X				1	15±3	±3	±3	±3	±3	±3	±3	Every 2 months (± 7 days)	Progression + - 7 ⁴		
Medical History ¹¹	X															
AE reporting			Recorded from Day 1 through 30 days after the last dose of study drug.													
Concomitant Medications			Recorded from the signing of the ICF through 30 days after the last dose of study drug.													
Physical Exam	X	X			X	X	X	X	X	X	X	X	X	X	X	X
Vital Signs ⁴	X	X			X	X	X	X	X	X	X	X	X	X	X	X
ECOG Performance Status	X	X			X	X	X	X	X	X	X	X	X	X	X	X
12-lead ECG ⁵	X	X				X				X		X	X ⁶			
Transthoracic echocardiogram (TTE) ⁶	X					X				X		X	X ⁶			
Comprehensive Geriatric Assessment	X										X					
Tissue for STAT 5 analysis ¹⁰	X															
Serum PSA	X	X				X	X	X	X	X	X	X	X	X	X	X
Serum Testosterone	X															
CBC w/ Diff	X	X			X	X	X	X	X	X	X	X	X	X	X	X
Blood Chemistry ⁸	X	X			X	X	X	X	X	X	X	X	X	X	X	X

Study Assessments	Screening		Cycle 1 ²	Cycle 2	Cycle 3	Cycle 4	Cycle 5	Cycle 6 and beyond (Treatment till progression)	End of treatment ¹ ² (EOT) visit	Follow-up (2 years) ³
	Each Cycle (28 days)		(in Days)		Every 2 months (± 7 days)		Every 2 months (± 7 days)	30-day post-last dose Safety Visit (±7 days)	Every 6 months post EOT visit (±21days)	
	Day -30 to -1	1	15±3	±3	±3	±3	±3	Progression +/ -		

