Coagulation (PT/PTT) and Hb A1C	X									
Research blood draw	X		X		X				X	
CT of Abdomen and Pelvis. /CT urogram/MRI abdomen and pelvis/PET ^{9, 13,15}	X				X				X	
Bone scan ^{9, 13,15}	X				X				X	
Chest Imaging ^{9,15}	X								X	
Pacritinib dispense	X ⁷		X ⁷	X	X	X ⁷	X ⁷		X	
Patient-reported outcome instrument: - FACT-P	X					X				

1. All screening procedures must occur within 30 days prior to treatment initiation.
2. Day 1 assessments are required to be performed prior to initiation of study treatment and can be performed up to 24 hours prior to initiation of study treatment. Study days are to be counted based on the start of treatment.
3. If a subject has disease progression or subject withdrawal, then they will be followed as per follow-up requirements. Patients will be in follow up for 2 years from EOT visit.
4. Vital signs include systolic and diastolic blood pressure, pulse, respiratory rate, temperature, and body weight.
5. A 12-lead ECG (collected in triplicate), including QTcF, will be performed at Screening, and then predose at C1D1, C2D1,, C5D1, C7D1, and every four months (every other cycle/odd cycles) thereafter provided normal QTcF.. if QTc is prolonged, more frequent monitoring will be done after discussion with sponsor. For patients who have discontinued treatment, ECGs are to be performed at the End-of-Treatment Visit but are not otherwise required
6. TTE will be performed at screening, C2D1, C5D1, C8D1, and every six months thereafter (every 3 cycles) provided normal LVEF and no

clinical evidence of heart failure. Window for all TTEs is -14 days from Day 1 of the cycle it is due for.

7. On days when ECGs are to be obtained, Pacritinib will be administered in the clinic to facilitate the performance of pre-dose assessments
8. Serum chemistry values will include AL T/SGPT, AST/SGOT, alkaline phosphatase, bilirubin (total, direct, and indirect) creatinine, LDH, sodium, potassium, chloride, bicarbonate, calcium, phosphate, magnesium, BUN/urea, albumin, glucose, cholesterol (fasting not required), and uric acid. Serum chemistry results obtained from unscheduled visits should be entered into the electronic database.
9. Additional serum chemistry testing should be done as clinically indicated.

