2.2 Secondary Objectives

1. To evaluate the absolute PSA nadir as a result of treatment which is expressed for each subject in the absolute value and as a percentage, change from baseline.
2. To determine the time to PSA nadir from the start of treatment. which is the lowest PSA on treatment.
3. To determine the time to next subsequent antineoplastic therapy.
4. To determine the effect of investigational treatment on testosterone levels which is assessed by the change of testosterone from baseline to cycle 4.
5. To determine the safety and toxicities of the study drug as assessed by CTCAE version 5.

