2.5 Secondary Endpoint(s)

1. Absolute PSA nadir.
2. Time to PSA nadir.
3. Time to next subsequent antineoplastic therapy.
4. Effect of investigational treatment on testosterone levels.
5. Safety and toxicities of the study drug.

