8.5 Analysis of secondary endpoints

The PSA nadir values will be summarized with mean and standard deviation as absolute values and as percent change from baseline PSA value. The time to PSA nadir and time to subsequent antineoplastic therapy will be summarized using Kaplan-Meier (KM) curves. The median will be estimated using the inverse-KM method and shown with 95% confidence intervals. The change in testosterone levels from baseline to cycle 4 will be shown graphically using box-plots and reported with mean and standard deviation.

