8.6 Analysis of exploratory endpoints

The analysis of Comprehensive Geriatric Assessment domains will be descriptive and will describe mean, median, standard deviations of scores at baseline and at follow up time points. CGA deficits over 6 months will be captured. Each domain will be evaluated individually, and scores will be compared between baseline and 6 months. Overall CGA deficits will be examined and the proportion of patients who decline in more than 1 domain will be determined for these time points.

For each of the 27 core items and 12 site-specific items of the FACT-P tool, mean score for the study cohort will be computed at baseline and at specified follow-up visits (Section 8). These means will be plotted against follow-up time and visually assessed for evidence of an upward or a downward trend. For each item, an upward or a downward trend in mean scores over time will indicate improvement or deterioration in a given dimension of quality of life (i.e., the dimension measured by that item). Changes in mean scores from baseline will be calculated at three months and six months after therapy initiation and will be reported with 95% confidence intervals.

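### Testosterone change to cycle 4 is a named secondary endpoint, but the study calendar schedules testosterone only at screening; the planned six-month FACT-P change likewise has no scheduled form

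*Combined protocol and SAP*

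**What the plan says.** **Testosterone.** Section 2.5 lists "Effect of investigational treatment on testosterone levels" as the fourth of five secondary endpoints. Section 2.2 fixes the measure: the effect is one "which is assessed by the change of testosterone from baseline to cycle 4". Section 8.5 gives the analysis: "The change in testosterone levels from baseline to cycle 4 will be shown graphically using box-plots and reported with mean and standard deviation". Section 8.10 adds that numeric secondary outcomes, testosterone among them, are analysed in patients with non-missing values, and that a change analysis needs a value at each of two time points.

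In the Study Calendar, the row "Serum Testosterone" has one mark, in the screening column. The rows for PSA, blood count and chemistry are marked through the treatment cycles.

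**FACT-P.** Section 8.6 says: "Changes in mean scores from baseline will be calculated at three months and six months after therapy initiation", with 95% confidence intervals. The calendar row "Patient-reported outcome instrument: - FACT-P" has two marks, one at screening and one during treatment.

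**The concern.** An endpoint defined as a change needs two measurements per patient, and the calendar is what sites work from. If it asks for testosterone only at screening, the eligibility value is collected and nothing can be paired with it.

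This matters beyond tidiness. Section 1.1 attributes the harms of androgen deprivation to low testosterone and argues from that for a non-hormonal alternative. The testosterone endpoint is where the trial would show that pacritinib leaves testosterone unchanged. A cycle 4 sample that was not drawn cannot be recovered later.

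For FACT-P, two post-baseline analysis times are promised and one post-baseline assessment is scheduled. One of the two planned changes, with its confidence interval, therefore has no scheduled source.

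**Working it through.** The plan states no sample size or power figure on this point, so there is none to reproduce. The check compares what the analysis needs with what is scheduled.

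**Testosterone: needed against scheduled**

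| Item | Source | Count |
|---|---|---|
| Values per patient needed for the change | Sections 2.2, 8.5, 8.10 | 2 (baseline, cycle 4) |
| Values per patient scheduled | Study Calendar, testosterone row | 1 (screening) |
| Scheduled pairs at cycle 4 | follows from the two rows above | 0 of up to 46 (0 of 10 in the first cohort) |

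Other places that could supply a second value:

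- Calendar footnotes: none adds a testosterone draw.
- Chemistry panel (calendar footnote 8): the analytes are listed and testosterone is not among them.
- Research blood (Section 4.5): plasma is for cell-free DNA and exosomes, and its analysis waits on a protocol amendment if a response is seen in the first 10 patients.
- Eligibility (inclusion criterion 8): a testosterone value above 50 ng/dL is required, but this is the screening value already counted.

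**FACT-P: needed against scheduled**

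Section 8.6 needs two post-baseline assessments, at three and six months. The calendar schedules one. Its visit can be placed in time from the 28-day cycle:

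Day 1 of cycle *c* falls (*c* − 1) × 28 days after the start of treatment; months = days / 30.4375.

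- Cycle 4: 3 × 28 = 84 days, or 2.8 months.
- Cycle 5: 4 × 28 = 112 days, or 3.7 months.
- Six months: 6 × 30.4375 = about day 183, between Cycle 7 Day 1 (day 168) and Cycle 8 Day 1 (day 196).

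Counting columns against the header puts the later FACT-P mark at cycle 4. It sits one column after the on-treatment imaging mark, however, and footnote 13 places that imaging at cycle 4, which would make the FACT-P visit cycle 5. On either reading it is near three months, and at least 183 − 112 = 71 days short of six months. Section 8.6 refers to follow-up visits specified in Section 8, but Section 8 contains no visit schedule.

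**Does the result depend on how the table was read?** The columns of the available text are shifted, so the visit attached to a mark can be uncertain. The finding rests on the number of marks. Where a row can be checked, the count is intact: the ECG row has six marks, and footnote 5 calls for six (screening, C1D1, C2D1, C5D1, C7D1 onwards, end of treatment). Sparse rows also kept isolated later marks; the geriatric assessment row and the FACT-P row each have one.

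**The case against.** There are four fair points on the other side.

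1. **The objective itself names cycle 4.** A site that reads Section 2.2 might draw the sample anyway, and routine-care values may exist for some patients. This stands as a matter of wording: the accurate statement is that no cycle 4 value is scheduled, and zero pairs follows only if the calendar is followed. It does not close the gap. Such values would be unsystematic, and the plan makes no provision for using them.

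2. **The FACT-P gap is smaller.** One post-baseline form is scheduled, so a change at about three months can be estimated, and the endpoint is exploratory and descriptive. This stands. Only the six-month change is unsupported.

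3. **The calendar text is damaged.** Header text has run into the consent row, and some footnote numbers do not match their notes. This justifies checking the source table. It does not show that a testosterone mark was lost, and no footnote suggests one.

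4. **The endpoint decides nothing.** It has no hypothesis test and no role in the futility or final decision. This is true, and it is why the point ranks below anything touching the primary endpoint. A named secondary endpoint should still be obtainable from the schedule.

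**Conclusion.** The concern holds. As written, the plan schedules one testosterone value per patient for an endpoint that needs two, so following the calendar yields 0 of up to 46 evaluable patients for secondary endpoint 4. For FACT-P, one of the two planned post-baseline times has a scheduled form, and the six-month change has none.

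This rests on the calendar marks being complete in the text available and on sites following the calendar. It does not rest on which column the later FACT-P mark belongs to. The primary endpoint and the safety assessments are unaffected. The correction should be made, ideally before more patients pass cycle 4.

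**What to change.** - **Check** the testosterone and FACT-P rows of the source calendar for lost marks.
- **Testosterone:** mark serum testosterone at the cycle 4 visit, and state in Section 8.5 which day of cycle 4 is meant and that the screening value is the baseline. If the sponsor does not want the sample, remove the change analysis from Sections 2.2, 2.5 and 8.5. That would reconcile the text, but it would leave the hormone-sparing rationale untested.
- **FACT-P:** either add a mark at a visit near six months (Cycle 7 Day 1 is day 168, Cycle 8 Day 1 is day 196) and state which visit serves as three months, or limit Section 8.6 to the one post-baseline visit collected. Replace the reference to Section 8 with a reference to the Study Calendar.

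The cost is one added assay on blood already drawn for PSA, blood count and chemistry, one repeat questionnaire if that option is taken, and a calendar amendment. Patients already past cycle 4 without a sample should be reported as missing for this endpoint.

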8.6 Analysis of exploratory endpoints

The analysis of Comprehensive Geriatric Assessment domains will be descriptive and will describe mean, median, standard deviations of scores at baseline and at follow up time points. CGA deficits over 6 months will be captured. Each domain will be evaluated individually, and scores will be compared between baseline and 6 months. Overall CGA deficits will be examined and the proportion of patients who decline in more than 1 domain will be determined for these time points.

For each of the 27 core items and 12 site-specific items of the FACT-P tool, mean score for the study cohort will be computed at baseline and at specified follow-up visits (Section 8). These means will be plotted against follow-up time and visually assessed for evidence of an upward or a downward trend. For each item, an upward or a downward trend in mean scores over time will indicate improvement or deterioration in a given dimension of quality of life (i.e., the dimension measured by that item). Changes in mean scores from baseline will be calculated at three months and six months after therapy initiation and will be reported with 95% confidence intervals.

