2.3 Exploratory Objectives

1. To determine if the study drug affects comprehensive geriatric assessment domains.
2. To determine if the study drug combination affects the quality of life.
3. To evaluate if positive status for Stat5 activation in the paraffin-embedded tissue sections of the diagnostic biopsies has a trend to predict biochemical response to pacritinib treatment.

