2.6 Exploratory Endpoints

1. Effect of pacritinib on CGA domains.
2. Effect of pacritinib on FACT-P score.
3. Effect of levels of Stat5 transcription factors in prostate cancer cells determined by fluorescence-based immunohistochemistry on biochemical responses response to pacritinib.
4. Identify biomarkers of response/resistance.

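### Section 8.6 plans FACT-P changes at three and six months, but the calendar as extracted marks FACT-P only once after baseline, and the FACT-P score named as the endpoint is never computed

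*Combined protocol and SAP*

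**What the plan says.** Section 2.6 lists as an exploratory endpoint the "Effect of pacritinib on FACT-P score". The Protocol Summary ties this to quality of life in both the short and the long term.

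Section 8.6 sets the analysis at item level: "For each of the 27 core items and 12 site-specific items of the FACT-P tool, mean score for the study cohort will be computed". The means are plotted over time and "visually assessed for evidence of an upward or a downward trend". One quality-of-life reading rule covers all items: "For each item, an upward or a downward trend in mean scores over time will indicate improvement or deterioration in a given dimension of quality". For the numerical result, "Changes in mean scores from baseline will be calculated at three months and six months after therapy initiation", with 95% confidence intervals. For the visits themselves, 8.6 refers the reader to Section 8.

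In the Study Calendar, the row "Patient-reported outcome instrument: - FACT-P" carries two marks as extracted, one at screening and one later. No footnote to the calendar mentions FACT-P.

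**The concern.** There are two separate problems.

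The first is collection. Two post-baseline changes are planned, but the calendar seems to schedule one post-baseline questionnaire. Sites work from the calendar, so a visit not marked there will not be collected, and it cannot be recovered afterwards.

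The second is the analysis variable. The endpoint is a score, but the analysis consists of separate item means. No total, domain score, scoring algorithm or item reversal is defined anywhere. Section 8.6 does treat the geriatric assessment by domain and overall, so FACT-P stands out. Anyone reporting a FACT-P score would have to choose its definition after seeing the data.

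The stake is modest but real. Section 1.1 motivates the trial partly by the quality-of-life burden of androgen deprivation, and FACT-P is the trial's named patient-reported instrument.

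**Working it through.** The plan gives no sample size, effect size, standard deviation (SD) or power for FACT-P, so it has no figure of its own to reproduce.

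**Visits needed against visits marked.** Section 8.6 needs baseline plus two later assessments. The calendar row shows screening plus one mark. The reference to Section 8 does not help: that is the statistical section itself, and its only FACT-P timing is the three- and six-month sentence in 8.6.

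**Does the column matter?** The extracted table is displaced, so each plausible column was tried. Cycles last 28 days, so Day 1 of cycle c falls (c − 1) × 28 days after the start. Months are days / 30.44.

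| Later mark belongs to | Time from start | Three-month change | Six-month change |
|---|---|---|---|
| Cycle 4 | 3 × 28 = 84 days, 2.8 months | available | no data |
| Cycle 5 | 4 × 28 = 112 days, 3.7 months | approximate | no data |
| Cycle 6 and beyond | first at 5 × 28 = 140 days, 4.6 months | no data | possible, if the single mark means repeated visits |

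Calendar footnote 13 places the mid-study imaging at Cycle 4, and the FACT-P mark sits one cell to the right of the imaging mark. This suggests Cycle 4 or 5 but does not settle it. At least one planned change is empty in every row. With baseline and one later visit, a trend over time is also just a single difference.

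**Unit of analysis.** 27 + 12 = 39 items are analysed separately, and no total is computed.

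**Size of the reporting caution.** Each item change has a 95% interval. With no true change and nominal coverage, the expected number of intervals excluding zero is 39 × 0.05 = 1.95, about 2, per collected visit. This is an expected count, so it does not require the items to be independent. For one total score it is 1 × 0.05 = 0.05 per visit.

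**Precision of a single total.** The half-width of a 95% interval for a mean change is t(0.975, n − 1) / √n, in SDs of the change:

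- n = 46 (full enrolment, all complete): 2.014 / 6.782 = 0.30
- n = 30 (an assumed number of completers): 2.045 / 5.477 = 0.37
- n = 10 (stop at the interim): 2.262 / 3.162 = 0.72

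**The case against.** The strongest reply is that this is an exploratory, descriptive endpoint read from a damaged table. No test, alpha or decision is attached to FACT-P. The word score in 2.6 does not say total, and 8.6 can be read as defining it through item mean scores. A single mark under Cycle 6 and beyond, headed as every two months, could stand for several questionnaires. Preferring a total scored by a manual that is not in the documents is a choice, not the correction of an arithmetical error.

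Much of this stands. The calendar must be checked against the original, and the count of one post-baseline FACT-P is provisional until then. The endpoint is better called under-specified than wrong. Neither point removes the mismatch: the repeated-visit reading leaves three months empty, and under-specification still leaves the scored variable to be chosen later.

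Four stronger readings are tempting but not supported:

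- A reader might treat all 39 × 2 = 78 intervals as independent tests and infer that a false signal is nearly certain. That counts a visit that appears not to be collected, assumes independence among items answered by the same men, and imposes an error rate that the plan does not claim.
- A reader might infer that the direction rule is wrong. The documents give neither item wording nor coding, so all that can be said is that the plan does not state whether items are recoded.
- A reader might infer that quality of life cannot be examined at all. Item means at baseline and at the collected visit can still be described.
- A reader might expect a better FACT-P score to show what is gained over androgen deprivation. The study has a single arm, so no scoring choice can do that.

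**Conclusion.** The point holds in two parts. First, 8.6 and the calendar as extracted cannot both be followed: at least one of the two planned FACT-P changes has no scheduled data. If the mark is at Cycle 4 or 5, the missing one is the six-month change, and the long-term part of the objective goes with it. This rests on the row having one later mark, to be confirmed in the original table, but not on which of the plausible columns holds it. Second, the endpoint is a score, but the analysis is 39 item means read by eye, with no total and no stated coding behind the direction rule.

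The multiplicity element is small: about two item intervals per collected visit excluding zero by chance, which is a caution for reporting and not a breach of error control. The primary endpoint is unaffected. The plan should be amended because a missed assessment cannot be recovered later and the remedy is cheap.

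**What to change.** 1. Check the FACT-P row in the original calendar. Then either mark FACT-P at existing visits near three and six months, or limit 8.6 to the visit actually collected. If the present mark is at Cycle 4 or 5, one addition near six months suffices, for example at Cycle 7 (168 days, 5.5 months), when an ECG is already due, or Cycle 8 (196 days, 6.4 months), when an echocardiogram is due.
2. Replace the reference to Section 8 with one to the Study Calendar.
3. Make change from baseline in the FACT-P total the main FACT-P analysis, with a 95% confidence interval, and cite the instrument's scoring manual, including any item reversal.
4. Present domain and item results as supportive, and apply the up-is-better rule only to scores coded so that higher is better.
5. Add a sentence that item intervals are descriptive and that about two per visit would exclude zero by chance.

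The cost is revised SAP wording, a calendar correction and at most one more questionnaire at an existing visit.

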8.2 Study hypotheses

The null hypothesis that the median PSA-progression-free survival is six months will be tested against a one-sided alternative by for the six-month PSA-progression-free survival probability exceeding 50%. The study is designed to have 80% power to obtain a result significant at a one-sided 10% level if the experimental treatment has a six-month PSA-progression-free probability of 66%, which corresponds to a median of 10 months if the time to PSA progression is exponentially distributed.(84)

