8.3 Study design and sample size

A two-stage single-arm design based on the methods of Huang et al (2010) will be used.

The design is based on a modification of a binomial two-stage design that allows the incorporation of data from subjects with less than six months of follow-up at the interim analysis. The study will enroll up to 46 subjects with an interim analysis performed when 10 patients have been treated and followed for 6 months. The underlying binomial design would stop for futility if there are four or fewer patients alive without PSA progression at six months among these 10 patients. The modified futility decision will use the Kaplan-Meier estimate of the six-month PSA-progression-free survival using the data from the first 10 subjects and any subject who have been enrolled during the six-month follow-up period of the tenth subject. If the six-month PSA-progression-free survival is significantly lower at a one-sided 10% significance level than the clinically meaningful value of 66% defined by the alternative hypothesis, the study will be stopped for futility. If no new patients would be enrolled during the follow-up period, this decision rule is equivalent to the one defined by the binomial design.

If the study is not stopped for futility, study enrollment continues until 46 subjects are enrolled. The final analysis will be performed when all subjects have been followed for at least six months. The null hypothesis will be rejected, and the study drug will be considered promising if 27 or more patients are alive without PSA progression at six months among the 46 patients. The underlying binomial design yields a type I error rate of 10% if the underlying six-month PSA-progression-free probability is 50% (and the median PSA-progression-free survival is 6 months), and power of 80% when the six-month PSA-progression-free probability is 66%, which corresponds to a median of 10 months if the time to PSA progression is exponentially distributed. Simulation studies confirmed that the design with the modified futility stopping method maintains these properties. If the median PSA-progression-free survival is six months, then the binomial design would stop at the interim analysis with 38% probability. Assuming an enrollment rate of 1.5 subjects/month, the modified futility stopping rule increases this probability of stopping at the interim analysis to 45%.

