8.10 Missing data

For all outcomes, summary statistics will include the count of missing and non-missing values. Patients with missing value for the primary outcome, PFS, will be censored at the time when last known to be alive and without progression. A similar approach will be used for other time-to-event outcomes, such as time to PSA nadir. Secondary outcomes requiring numeric values, such as geriatric assessments, PSA and testosterone levels will be analyzed among patients with non-missing values as required for each analysis (e.g., non-missing value at specific time point for cross-sectional analysis, and non-missing values at two time points for change analyses). The limitations of extensive missingness, if present, will be clearly noted in all reports and any related findings will be interpreted with caution.

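### The FACT-P plot of visit means can show a trend when no man has changed, because later means may come from fewer and different men; the reading should rest on within-patient change

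*Combined protocol and SAP*

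**What the plan says.** Section 8.6 takes the mean score of the study cohort on each of the 39 FACT-P items (27 core, 12 site-specific) at baseline and at later visits. "These means will be plotted against follow-up time and visually assessed for evidence of an upward or a downward trend". The next sentence treats such a trend as improvement or deterioration in that dimension of quality of life. The section also asks for changes from baseline at three and six months with 95% confidence intervals. For the geriatric assessment it compares baseline with six months by domain and adds that "the proportion of patients who decline in more than 1 domain will be determined for these time points".

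Section 8.10 analyses numeric outcomes among patients with data, which means "non-missing value at specific time point for cross-sectional analysis, and non-missing values at two time points for change analyses". It also promises counts of missing and non-missing values, and a caution in reports if missingness is extensive. It plans no model, imputation or sensitivity analysis for these scores.

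Under section 3.1 treatment ends at progression, intolerable adverse events, withdrawal or new prostate cancer therapy. Footnote 3 of the Study Calendar then moves the man to the follow-up schedule. Section 4.6 keeps him on study, with procedures done as the protocol indicates. In the calendar as extracted, the FACT-P and geriatric rows each show screening and one later mark, apparently mid-treatment. Neither shows a mark at end of treatment or follow-up.

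**The concern.** A plot of cross-sectional means compares the baseline mean of all men with a later mean of the men who still have a score. If men who leave differ at baseline from men who stay, the curve moves even when no individual score does, and section 8.6 would report that movement as a change in quality of life. With one arm, no comparator would reveal the artefact.

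The geriatric proportion has a related problem. It is a within-patient measure, but men without the later assessment drop out of it, so it describes only those who remained.

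Section 1.1 argues for a non-hormonal drug largely from the harm that androgen deprivation does to function and quality of life in older men. These results are therefore likely to be cited, although section 2.6 lists them as exploratory.

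**Working it through.** **Inputs from the documents.** Section 8.2 sets "The null hypothesis that the median PSA-progression-free survival is six months", so S(6) = 0.50 under the null. Under the alternative the "experimental treatment has a six-month PSA-progression-free probability of 66" per cent, said to match an exponential median of 10 months. Section 8.3 gives N = 46. Section 4.6 requires a PSA rise after an initial decline to be confirmed at least three weeks later. Cycles last 28 days.

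**Inputs assumed.** The baseline gap g between men who stay and men who leave is 0.3-0.5 SD; the documents give neither its size nor its sign. Event times are exponential for any time other than six months.

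**The plan's figure.** 0.5^(6/10) = 0.660, so 66% and a 10-month median agree.

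**Share progressed or dead by six months, 1 - S(6).**
- Alternative: 1 - 0.66 = 0.34, or 0.34 × 46 = 15.6 men.
- Null: 1 - 0.50 = 0.50, or 23 men.

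**With the three-week confirmation lag.** 21/30.4375 = 0.69 months, so use S(5.31).
- Alternative: 1 - 0.66^(5.31/6) = 0.308.
- Null: 1 - 0.50^(5.31/6) = 0.459.

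**At Cycle 5 Day 1**, the likeliest place of the one later FACT-P mark: 4 × 28 = 112 days, and 112/30.4375 = 3.68 months.
- Alternative: 1 - 0.66^(3.68/6) = 0.225.
- Null: 1 - 0.50^(3.68/6) = 0.346.

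These Cycle 5 shares may be too high, because section 4.6 plans to continue treatment through early PSA rises for at least 12 weeks.

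**Artefact when no man changes.** Let m be the share without a later score and μ the mean of those who stay. The baseline mean of all men is μ - m·g and the later available-case mean is μ, so the plotted shift is m·g.

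| m | g = 0.3 SD | g = 0.5 SD |
|---|---|---|
| 0.34 | 0.10 SD | 0.17 SD |
| 0.50 | 0.15 SD | 0.25 SD |

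If those who leave score higher at baseline, the shift has the same size and points down.

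As a yardstick, the standard error of the later mean is 1/√30.4 = 0.18 SD at m = 0.34 and 1/√23 = 0.21 SD at m = 0.50. The shift is thus about 0.10/0.18 = 0.6 to 0.25/0.21 = 1.2 standard errors.

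**Paired change in the same scenario.** It is zero, because each man is compared with himself. A simulation of 46 men with g = 0.5 SD and zero-mean individual change (SD 0.6) gave unpaired shifts of 0.173 and 0.249 SD at m = 0.34 and 0.50. The paired change was 0.000 in both.

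**The case against.** Most of the opposing case stands as a limit on the point.

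- A reader might infer that the plan collects FACT-P and geriatric scores only on treatment. No sentence says so. It is inferred from calendar rows whose alignment was lost, although other rows in the same tables do carry late marks.
- A reader might take 34-50% as the share of men who cannot be scored at six months. It is the design's assumed rate of PSA progression or death, not a missing-data rate. The calendar also does not visibly contain a six-month assessment.
- It is tempting to add the 17.4% discontinuation for adverse events in the PAC203 summary (section 1.5.4). That rate pools three dose arms in myelofibrosis after ruxolitinib failure or intolerance and has no six-month time base. Toxicity stops would add to the loss, but the documents give no amount for this population.
- A reader might infer that the bias favours the drug. A man stopping for a PSA rise need not feel or function worse, and section 1.1 describes many older patients as without symptoms. The direction is not established.
- Section 8.10 requires both values for a change analysis, which removes the composition artefact there.
- Section 8.10 also promises missing-value counts and cautious interpretation. That warns the reader but does not correct a plot whose trend section 8.6 tells the analyst to read as real.

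What survives is that the trend rule in section 8.6 does not use the paired analysis, and that nothing accounts for men who left.

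**Conclusion.** The point holds in a limited form. Followed as written, sections 8.6 and 8.10 can report a quality-of-life trend when no man has changed. From progression alone the artefact is about 0.10-0.25 SD. That rests on the design's 66% and 50%, an assumed gap of 0.3-0.5 SD of unknown sign, and the reading that nothing is assessed after treatment ends. With the confirmation lag the share lost is 31-46%; at Cycle 5 Day 1 it is about 22-35%, possibly less.

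The documents do not support a claim that every change analysis is distorted. Paired changes are free of this artefact, but they and the geriatric decline proportion describe only men who remained. Section 8.6 also leaves open whether its changes at three and six months are paired or differences between two visit means.

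The endpoints are exploratory with no decision rule, so this is a cheap improvement of modest priority. It is separate from the mismatch between the three- and six-month analyses and the single visible post-baseline mark. Reconciling those would not cure this problem.

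**What to change.** In section 8.6:

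1. Base the trend reading on within-patient change and state that the changes at three and six months are paired. Alternatively, use a repeated-measures mixed model that includes every man with a baseline score. FACT-P total and subscale scores are preferable to 39 separate items.
2. Print the number of men contributing at each visit on the plot, so that the counts promised in section 8.10 appear beside the means.
3. Report the geriatric result over all treated men in three groups: declined in more than one domain, did not decline, and off treatment or dead before the assessment.

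As an option, collect FACT-P at the existing end-of-treatment visit. That visit falls 30 days after the last dose and at a different time for each man, so it does not replace a six-month value.

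The cost is revised wording and a little more analysis, plus one self-completed form if the option is taken. The mixed model relies on data being missing at random, which cannot be checked here. The quality-of-life result may look less favourable.
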